APPENDIX C: LISTING LAYOUTS

**Listing
Subject Disposition**

Subject	ITT[1]	Safety[2]	Evaluable[3]	Replaced[4]	Concentration of Nickel Sulfate Used	First Injection Date	Last Injection Date	Total # of Injection(s)	Complete?	Primary Reason for Not Completing
---------	--------	-----------	--------------	-------------	--------------------------------------	----------------------	---------------------	-------------------------	-----------	-----------------------------------

[1] Intent to Treat (ITT): Enrolled subjects who signed informed consent.

[2] Received at least one dose of study drug.

[3] An evaluable subject is one who has completed dosing (or prematurely discontinued the administration due to a toxicity) and has undergone sufficient assessments to allow an assessment of the tolerability of the administration.

[4] Enrolled subjects but not meeting the criteria of evaluable.

path\t_program.sas date time

**Listing
Inclusion/Exclusion Criteria
Part 1 of 4**

Inclusion Criteria:

1:
2:
3:
4:
5:
6:
7:
8:

Exclusion Criteria:

1:
2:
3:
4:
5:
6:
7:
8:
9:
10:
path\t_program.sas date time

Listing 2(cont.)
Inclusion/Exclusion Criteria
Part 2 of 4: Inclusion Criteria

Subject	Date Informed Consent Signed	Inclusion Criteria							
		1	2	3	4	5	6	7	8

path\t_program.sas date time

Listing 2(cont.)
Inclusion/Exclusion Criteria
Part 3 of 4: Exclusion Criteria

Subject	Date Informed Consent Signed	Exclusion Criteria									
		1	2	3	4	5	6	7	8	9	10

path\t_program.sas date time

Listing 2(cont.)
Inclusion/Exclusion Criteria
Part 4 of 4: Waiver

Subject	Comply with ALL Entry Criteria	Entry Criteria Not Met	Exemption Explanation	Exemption Granted By	Date

path\t_program.sas date time

Listing 3
Demographics

Subject	Date of Birth	Age	Sex	Ethnicity	Race
----------------	----------------------	------------	------------	------------------	-------------

[1] Age is calculated by comparing the date of birth and the informed consent date.
path\t_program.sas date time

Listing 4
Medical History

Subject	Mark if None	MH #	Body System	Description	Diagnosis/Onset	Mark if Ongoing
---------	--------------	------	-------------	-------------	-----------------	-----------------

path\t_program.sas date time

Listing 5
Hematology and CBC with Differential
Part 1 of 2

Subject	Visit	Mark if Not Done	Not Done Reason	Collection Date/Time	WBC (X1000/uL)	RBC (XMil/uL)	Hemoglobin (g/dL)	Hematocrit (%)	Platelets (X1000/uL)	Neutrophils (segs) (%)	Neutrophils (bands) (%)
---------	-------	------------------	-----------------	----------------------	----------------	---------------	-------------------	----------------	----------------------	------------------------	-------------------------

Note: A result marked with “**” indicates a result that is abnormal and clinically significant.
path\t_program.sas date time

Listing 5 (cont.)
Hematology and CBC with Differential
Part 2 of 2

Subject	Visit	Mark if Not Done	Not Done Reason	Collection Date/Time	Lymphocytes (%)	Monocytes (%)	Eosinophils (%)	Basophils (%)	Other
---------	-------	------------------	-----------------	----------------------	-----------------	---------------	-----------------	---------------	-------

Note: A result marked with “**” indicates a result that is abnormal and clinically significant.
path\t_program.sas date time

Programmer note: for “other”, put test name instead of “other” in the column name.

Listing 6
Lab Normal - Hematology

Lab Test	Sex	Lab		Lab Units	If Other, Specify
		Low	High		
WBC				X1000/uL	

path\t_program.sas date time

Listing 7
Pregnancy Test

Subject	Visit	Mark if Not Done	Not Done Reason	Collection Date	Sample Type	Result
----------------	--------------	-----------------------------	----------------------------	------------------------	--------------------	---------------

path\t_program.sas date time

**Listing
ICDRG Score [1]**

Subject	Visit	Treatment Date	Treatment Regimen 1				Treatment Regimen 2			
			TR 1-1	TR 1-2	TR 1-3	TR 1-4	TR 2-5	TR 2-6	TR 2-7	TR 2-8
	Day 3		? (A)		+ (P) *					
	Day 4									

Note: A= rHuPH20; P= Placebo

Note: Results marked with "*" indicate Maximal Severity Score.

[1] ICDRG Score:

Score (Grade)	Score Interpretation
?	(1/2) Doubtful reaction; faint macular erythema only
+	(1) Weak (nonvesicular) positive reaction; erythema infiltration, possibly papules
++	(2) Strong (vesicular) positive reaction; erythema, infiltration, papules, vesicles
+++	(3) Extreme Positive reaction; bullous reaction
-	(0) Negative reaction
IR	(NA) Irritant reaction of different types

path\t_program.sas date time

Programmer Note: Each subject will have one Maximal Severity Score marked for each injection type (for a total of 2 scores marked per subject).

Listing
TEWL (Trans-Epidermal Water Loss) Assessment (g/m²h)

Subject	Visit	Was TEWL Completed?	Collection Date/Time	Result							
				TR 1-1	TR 1-2	TR 1-3	TR 1-4	TR 2-5	TR 2-6	TR 2-7	TR 2-8
	Day 1										
	Day 3										
	..										

path\t_program.sas date time

Listing 45
Digital Photographs

Subject	Visit	Were Digital Photos Taken?	Collection Date	Collection Time	Uploaded to Website?
		No:reason			No:reason

path\t_program.sas date time

Listing 46
Chromometer
Part 1 of 3: a-Scale

Subject	Visit	Was a Chromometer Reading Completed?	Collection Date	Collection Time	Category	TR 1-1	TR 1-2	TR 1-3	TR 1-4	TR 2-5	TR 2-6	TR 2-7	TR 2-8
	Day 1	No:reason											
	Day 3				Result Change from Day 1								

path\t_program.sas date time

Listing 11
Chromometer
Part 2 of 3: b-Scale

Subject	Visit	Was a Chromometer Reading Completed?	Collection Date	Collection Time	Category	TR 1-1	TR 1-2	TR 1-3	TR 1-4	TR 2-5	TR 2-6	TR 2-7	TR 2-8
	Day 1	No:reason											
	Day 3				Result Change from Day 1								

path\t_program.sas date time

Listing 11
Chromometer
Part 3 of 3: l-Scale

Subject	Visit	Was a Chromometer Reading Completed?	Collection Date	Collection Time	Category	TR 1-1	TR 1-2	TR 1-3	TR 1-4	TR 2-5	TR 2-6	TR 2-7	TR 2-8
	Day 1	No:reason											
	Day 3				Result Change from Day 1								

path\t_program.sas date time

Listing 47
Subject Diary

Subject	Visit	Mark if Not Done	Not Done Reason	Date	Start Time	End Time	Symptom	Severity[1]	Comments	Dispense next Diary to subject?
						ongoing				

[1] 1 – Least Discomfort, 5 – Most Discomfort.

path\t_program.sas date time

Listing 48
Screening Nickel Sulfate and Vehicle Control Patches

Subject	Application of Patches				Test Results (48 Hours After Application)						
	Patches Applied?	Date	Time	Date	Time	48 hours After App.?	ICDRG			Dose Assigned?	Assigned Dose
No:reason				No:reason				No:reason			No:reason
path\t_program.sas	date	time					1%	2.5%	5%		

Listing 49
Study Drug Administration – Treatment Regimen 1
Part 1 of 4: Application of Nickel Sulfate Patches

Subject	Visit	Treatment Date	8 Areas Normal?	Application Time	4 Patches applied?	Concentrations of Nickel Sulfate
No:reason						

path\t_program.sas date time

Listing 14 (cont.)
Study Drug Administration – Treatment Regimen 1
Part 2 of 4: Physical Examination Prior to Injection

Subject	Visit	Subject Randomized?	Treatment Date	Asse. Time	ICDRG Score				AE #			
					TR 1-1	TR 1-2	TR 1-3	TR 1-4	TR 1-1	TR 1-2	TR 1-3	TR 1-4
									None	None	None	None

path\t_program.sas date time

Listing 14 (cont.)
Study Drug Administration – Treatment Regimen 1
Part 3 of 4: Study Drug Administration

Subject	Visit	Treatment Date	TR 1-1		TR 1-2		TR 1-3		TR 1-4	
			Drug Injected?	Time						
No:reason										

path\t_program.sas date time

Listing 14 (cont.)
Study Drug Administration – Treatment Regimen 1
Part 4 of 4: Physical Examination and Safety Review after Injection

Subject	Visit	Treatment Date	Test Category	Asse. Time	AE #			
					TR 1-1	TR 1-2	TR 1-3	TR 1-4
			Physical Exam. (10 mins. Post) Safety Review (30 mins Post)	None	None	None	None	None

path\t_program.sas date time

Listing 15
Study Drug Administration – Treatment Regimen 2
Part 1 of 4: Physical Examination Prior to Injection

Subject	Visit	Subject Randomized?	Treatment Date	Asse. Time	ICDRG Score				AE #			
					TR 2-5	TR 2-6	TR 2-7	TR 2-8	TR 2-5	TR 2-6	TR 2-7	TR 2-8
									None	None	None	None

path\t_program.sas date time

Listing 15 (cont.)
Study Drug Administration – Treatment Regimen 2
Part 2 of 4: Study Drug Administration

Subject	Visit	Treatment Date	TR 2-5		TR 2-6		TR 2-7		TR 2-8	
			Drug Injected?	Time						
No:reason										

path\t_program.sas date time

Listing 15 (cont.)
Study Drug Administration – Treatment Regimen 2
Part 3 of 4: Physical Examination and Safety Review after Injection

Subject	Visit	Treatment Date	Test Category	Asse. Time	AE #			
					TR 2-5	TR 2-6	TR 2-7	TR 2-8
			Physical Exam. (10 mins. Post) Safety Review (30 mins Post)		None	None	None	None

path\t_program.sas date time

Listing 15 (cont.)
Study Drug Administration – Treatment Regimen 2
Part 4 of 4: Application of Nickel Sulfate Patches

Subject	Visit	Treatment Date	Application Time	Mark if Not Done	4 Patches	Not applied Reason	Concentrations of Nickel Sulfate
---------	-------	----------------	------------------	------------------	-----------	--------------------	----------------------------------

path\t_program.sas date time

Listing 16
Adverse Events

Subject	Mark if None	AE Term	Start Date/Time	Resolved Date/Time	Serious	Severity (CTCAE3)	Action Taken with Study Drug	Relationship to Study Drug	Other Action Taken	Outcome
---------	--------------	---------	-----------------	--------------------	---------	-------------------	------------------------------	----------------------------	--------------------	---------

path\t_program.sas date time

Listing 17
Serious Adverse Events

Subject	Mark if None	AE Term	Start Date/Time	Resolved Date/Time	Severity (CTCAE3)	Action Taken with Study Drug	Relationship to Study Drug	Other Action Taken	Outcome
---------	--------------	---------	-----------------	--------------------	-------------------	------------------------------	----------------------------	--------------------	---------

path\t_program.sas date time

Listing 18
Vital Signs

Subject	Visit	Mark if Not Done	Not Done Reason	Visit Date	Category	Visit Time	Heart Rate (bpm)	Blood Pressure (mmHg)	Respiration (breaths/min)	Body Temperature (°F)
Screening										
	Day 1				Pre-injection					
					Post-injection					
	...									
	Day 14									

path\t_program.sas date time

Listing 19
Physical Examination

Subject	Visit	Mark if Not Done	Not Done Reason	Date of Exam	Any Change from Previous Exam	Body System	Result	Description of Abnormality
							Normal	
							Abnormal	
							Abnormal, Clinically Significant	

path\t_program.sas date time

Listing 20
Comments

Subject	Mark if None	Comment #	Pertains to Visit Date	CRF Page	Comment
---------	-----------------	-----------	---------------------------	----------	---------

path\t_program.sas date time

Listing 21
Prior and Concomitant Medications

Subject	Mark if None	CM #	Medication	Indication	Start Date	Stop Date	Dose	Unit	Route	Frequency	Taken for AE?	AE #
						ongoing						

path\t_program.sas date time

Listing 22
Deaths

Subject	Date of Death	Date Death Reported to Site	Primary Cause of Death	Was Autopsy Performed?	Comment	Signature of Investigator	Signature Date
---------	---------------	-----------------------------	------------------------	------------------------	---------	---------------------------	----------------

path\t_program.sas date time

Listing 23
Subject Visit

Subject	Initials	Visit	Visit Date
----------------	-----------------	--------------	-------------------

path\t_program.sas date time

APPENDIX D: FIGURE LAYOUTS

Figure 1

ICDRG Scores- Subject 001XXX

Regimen 1			
++ P	++ A	++ P	++ A
Regimen 2			
++ P	++ A	+++ P	++ A

Day 3

Regimen 1			
++ P	++ A	++ P	++ A
Regimen 2			
++ P	++ A	++ P	++ A

Day 4

Regimen 1			
++ P	++ A	++ P	++ A
Regimen 2			
++ P	++ A	++ P	++ A

Day 5

Regimen 1			
++ P	++ A	++ P	++ A
Regimen 2			
++ P	++ A	++ P	++ A

Day 6

Regimen 1			
++ P	++ A	++ P	++ A
Regimen 2			
++ P	++ A	++ P	++ A

Day 7

Regimen 1			
++ P	++ A	++ P	++ A
Regimen 2			
++ P	++ A	++ P	++ A

[figure not shown]
Day 14

Note: A= rHuPH20, P= Placebo, NR= Not Reported.

Only subjects reported in both the Demographic and ICDRG datasets are considered.

[figure not shown]
Regimen 1 from left to right- TR1-1, TR1-2, TR1-3, TR1-4 and Regimen 2 from left to right- TR2-5, TR2-6, TR2-7, TR2-8
path\program.sas date time

Figure 2
Individual TEWL Scores by Day and Injection Site
Subject 001XXX- Regimen 1

Note: A= rHuPH20, P= Placebo.
path/program.sas date time

Figure 3
Individual a-Scale Chromometer Baseline Corrected Scores by Day and Injection Site
Subject 001XXX- Regimen 1

Note: A= rHuPH20, P= Placebo.
path/program.sas date time

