#### **6.4. Randomization and Blinding**

This is a double-blind randomized study. Subjects and the investigative staff will be blinded to the contents of each study drug injection. The pharmacist or designee at the investigative site preparing syringes for injection will not be blinded. The randomization list will be provided by the designated data management team. When a subject is randomized in the study, they must always be assigned to the lowest randomization number (e.g., subject number) available at the time of randomization.

Replacement subjects will be added if a subject discontinues prior to fulfilling the evaluability criteria ([Section 5.2](#)). Replacement subjects must always be assigned to the lowest available subject ID number available from the replacement randomization code.

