#### **6.5. Unblinding Procedures**

The randomization code will be kept in a secure, limited-access area, so that no one other than the pharmacist or designee preparing the syringes has access. The rest of the investigational staff, the study subjects, and the Sponsor and representatives of the Sponsor will not have access to the randomization code until the study as a whole has been unblinded, after the last data have been collected for the last subject in the study.

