4. GENERAL ANALYSIS CONSIDERATIONS

The statistical analyses will be reported using summary tables, figures, and data listings. Descriptive statistics will be used to summarize all efficacy variables. No formal statistical comparisons between treatments are planned. Continuous variables will be summarized with means, standard deviations, medians, minimums, and maximums. Categorical variables will be summarized by counts and by percentage of subjects in corresponding categories.

Individual subject data obtained from the case report forms (CRFs), local lab and any derived data will be presented by subject in data listings.

The analyses described in this plan are considered a priori, in that they have been defined prior to database lock and prior to breaking the blind. Any analyses performed subsequent to breaking the blind will be considered post-hoc. Post-hoc analyses will be identified in the CSR.

All analyses and tabulations will be performed using SAS® Version 9.1 on a PC platform. Tables and listings will be presented in RTF format. Figures will be presented in PDF format. Upon completion, all SAS® programs will be validated by an independent programmer. In addition, all program output will undergo a senior level statistical review. The validation process will be used to confirm that statistically valid methods have been implemented and that all data manipulations and calculations are accurate. Checks will be made to ensure accuracy, consistency with this plan, consistency within tables, and consistency between tables and corresponding data listings. Upon completion of validation and quality review procedures, all documentation will be collected and filed by the project statistician or designee.

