9.1 Statistical Analyses

The primary analysis is the pair-wise intra-subject comparison of endpoint parameters for the injections with and without rHuPH20. The secondary analysis covers safety and other endpoint parameters (see Section 10).

ICDRG scores will be shown for Treatment Regimen 1 and Treatment Regimen 2 by injection types (rHuPH20 or Placebo) at Baseline, Day 4, Day 5, Day 6, Day 7 and Day 14. ICDRG scores will be reported by subject using figures (Figure 1) and listings (Listing 8).

A qualitative medical review of the ICDRG scores will be used to investigate:

- Possible treatment effect of rHuPH20 or placebo control injection on the exposure to topical nickel allergen.
- Proportion of subjects that have a ≥ 1 grade reduction in at least one patch region.

At the conclusion of the study, findings from the medical review will be summarized in the clinical study report.

For Treatment Regimen 2, the day of maximal ICDRG Score will be used to assess the possible effect each injection type has on the onset of reaction to topical nickel allergen. The day of maximal ICDRG Score will be summarized for each injection type using counts and percentages (Table 6.1/6.2). Possible days of maximal ICDRG Score include

the following: Day 4, Day 5, Day 6, Day 7, and Day 14. If the maximal ICDRG Score for an injection type occurred prior to treatment, the subject will be reported as never having had an ICDRG Score more severe than Day 3 for summary purposes.

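### The medical review of ICDRG scores has no preset criteria, its named displays show the treatment beside each score, and no masked reading is planned

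*SAP*

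**What the plan says.** SAP section 4 states: "No formal statistical comparisons between treatments are planned". For the ICDRG score, section 9.1 first names the displays: "ICDRG scores will be reported by subject using figures (Figure 1) and listings (Listing 8". The next paragraph gives the task of judging them: "A qualitative medical review of the ICDRG scores will be used to investigate" a possible treatment effect and the proportion of subjects with a reduction of at least one grade. It then says: "At the conclusion of the study, findings from the medical review will be summarized in the clinical study report".

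Both displays identify the treatment. The Figure 1 layout in Appendix D carries the note "Note: A= rHuPH20, P= Placebo, NR= Not Reported" and prints the letter in every cell. The ICDRG listing in Appendix C carries "Note: A= rHuPH20; P= Placebo" and prints the letter beside the score.

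The trial's own blind is set out in the protocol. Section 6.4 says: "Subjects and the investigative staff will be blinded to the contents of each study drug injection". Section 6.5 keeps the randomization code closed to them "until the study as a whole has been unblinded, after the last data have been collected for the last subject in the study".

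**The concern.** With no formal comparison, a reader's judgement carries the ICDRG conclusion, and the SAP gives that reader no rule. Each regimen has two rHuPH20 and two placebo sites per subject. Nothing says how to weigh two drug sites that disagree, a difference that appears on one day only, or a late change. Protocol section 8 states the expected direction: rHuPH20 better than placebo. A reader who knows that direction and sees the letters can, in good faith, resolve unclear patterns towards it.

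At stake is how credible a positive finding would be. Blinded scoring protects each recorded score, but not the step from scores to conclusion. A critic could discount the finding for that reason even if the drug works.

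**Working it through.** The plan gives no figure to reproduce on this point. The sample size of 20 evaluable subjects (SAP section 11) has no alpha, power, effect size or variance behind it. The check is therefore mainly of the text, with a count of labels and one illustration.

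**1. What else could support an ICDRG conclusion?** The SAP's list of tables has one ICDRG table: Table 6, day of maximal score, for Treatment Regimen 2 only. TEWL and chromometer readings are separate measures. For Regimen 1 the medical review is the only stated route to a conclusion on ICDRG.

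**2. What would the reviewer see?** Section 9.1 names Figure 1 and Listing 8 for the scores, and both carry the treatment letter. Listing 14 (Part 2) and Listing 15 (Part 1) show ICDRG scores by site position without letters, but section 9.1 does not mention them. Neither document describes a masked display, a masked reader, a second reader or a decision rule.

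**3. Is the review prespecified?** SAP section 4 treats the planned analyses as a priori because they were defined before the blind is broken. For this review, its existence is defined but its criteria are not. Under protocol section 6.5, lettered outputs for the reviewer can exist only after unblinding.

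**4. How many scores are labelled?**
- Per subject: 8 sites x 6 days (3, 4, 5, 6, 7, 14) = 48. In the Figure 1 layout all 48 cells are labelled, 24 A and 24 P.
- For 20 evaluable subjects: 48 x 20 = 960.
- Regimen 1 scores on Day 3 precede any injection at those sites: 4 x 20 = 80. They carry no treatment contrast.
- Remaining: 960 - 80 = 880. Regimen 2 scores on Day 3 stay in, because those sites were injected on Day 1.

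**5. How sensitive could such a reading be?** This is an illustration, not an estimate. Assume 20 independent subjects, one regimen, one call per subject on which pair of sites did better, no drug effect, and a rule that at least 15 of 20 calls must favour rHuPH20. None of this is in the documents.
- Masked reader: each call favours rHuPH20 with p = 0.5, and P(X >= 15 | n = 20, p = 0.5) = 0.0207. A 14-of-20 rule would give 0.0577.
- Reader who sees the letters and gives every tie to rHuPH20: with tie share t, p = (1 - t)/2 + t.

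| Tie share t | p | P(X >= 15 of 20) |
|---|---|---|
| 10% | 0.55 | 0.055 |
| 20% | 0.60 | 0.126 |
| 30% | 0.65 | 0.245 |
| 50% | 0.75 | 0.617 |

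The documents give no tie share and no reason to assume that every tie would go one way. The table shows only that a modest lean matters when the number of subjects is small.

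**The case against.** The strongest reply is that lettered outputs are ordinary results produced after unblinding. A within-subject comparison must reveal the treatment at some point, and reading a figure cannot alter a recorded score. That stands. A reader might infer that the double blind is broken, and the documents do not support this: staff who score the sites are blinded, and the code is withheld until the last data are in.

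A reader might also infer that the SAP requires an unmasked reviewer to read Figure 1. It does not say so. It speaks of a review of the scores and is silent on who reads and whether that person is masked. That the lettered displays are the ones read is a strong inference from section 9.1, since it names no others for these scores.

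Nor do the documents support calling the review the whole efficacy conclusion, or the trial's most subjective step. Section 9.1 says only that it will investigate a possible effect. Table 6 addresses onset in Regimen 2 by a fixed rule, TEWL and chromometer values come from instruments, and bedside ICDRG scoring is itself a visual judgement. The share of subjects with a one-grade reduction is largely a count on the fixed grades of SAP section 8.1, against the Day 3 baseline of section 8.4. Under those grades a doubtful and a negative reaction differ by a set half grade, so that pair is not ambiguous.

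Finally, the missing decision rule can be seen as the root problem: a prespecified within-subject summary would turn the review into commentary. That is largely fair, but no such summary is planned, and masking would still improve whatever review remains.

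**Conclusion.** The point holds as a limitation of the planned reading, not as a breach of the blind. The ICDRG treatment-effect conclusion comes from a review without preset criteria, its named displays show the allocation, and no masking is planned. Exposure is greatest for Regimen 1. In Regimen 2, Table 6 gives partial support, on onset only.

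The labelling covers every subject and both regimens, but the count measures exposure and not bias. The size of the bias cannot be derived from the documents. The conclusion assumes that the reviewer works from the displays named in section 9.1; if an unstated procedure already masks the reviewer, the SAP need only say so. For a small descriptive pilot this is a worthwhile, inexpensive improvement, not the correction of an error or contradiction.

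**What to change.** Amend SAP section 9.1 and the layouts in Appendices C and D as follows.

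1. Produce Figure 1 and Listing 8 first with A and P replaced by X and Y, assigned at random per subject and regimen. A programmer or code holder who is not the medical reviewer prepares them.
2. For each subject and regimen, the reviewer records one of three calls: X better, Y better, or no difference. Regimen 1 is judged on change from Day 3. The reviewer signs the calls before decoding.
3. After decoding, the clinical study report tabulates the calls by true treatment for each regimen.
4. Release the lettered Figure 1 and Listing 8 only after sign-off, as reference outputs.

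With no drug effect, X and Y calls should favour each treatment about equally often, so the tabulation also gives a countable result where the plan has only a narrative.

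The cost is SAP wording, one further run of an existing figure and listing program, and a short sequencing step. It also needs a documented separation between code holder and reviewer, reconciled with the access limits in protocol section 6.5. No new data, visits or additional reader are needed.
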